| CRC | Clinical Research Center |
| DEXA | Dual Energy X-ray Absorptiometry |
| DSMB | Data and Safety Monitoring Board |
| EMSA | Electrophoretic Mobility Shift Assay |
| FDA | Food and Drug Administration |
| FE _L | Hepatic Fractional Extraction |
| HBSS | Hank's Buffered Saline Solution |
| HIPAA | Health Insurance Portability and Accountability Act |
| HCG | Human Chorionic Gonadotropin |
| HCG-ST | Human Chorionic Gonadotropin Stimulation Test |
| HPF | Hepatic Plasma Flow |
| ICD | Informed Consent Document |
| IDS | Investigational Drug Service |
| IND | Investigational New Drug |
| ICL | Integrative Physiology Laboratory |
| IR | Insulin Resistance |
| ISR | Insulin Secretion Rate |
| IRB | Institutional Review Board |
| IUD | Intrauterine Device |
| K _m | Hepatic Insulin Delivery Rate |
| LH | Luteinizing Hormone |
| MNC | Mononuclear Cells |
| MRI | Magnetic Resonance Imaging |
| NF _κ B | Nuclear Factor κ B |
| OCC | Outpatient Care Center |
| OGTT | Oral Glucose Tolerance Test |
| 17OHP | 17-Hydroxyprogesterone |
| PHI | Protected Health Information |
| PI | Principal Investigator |
| PCOS | Polycystic Ovary Syndrome |
| ROS | Reactive Oxygen Species |
| RT-PCR | Real-Time Polymerase Chain Reaction |
| S _I | Fractional Glucose Disappearance/Insulin Concentration Unit |
| UIC | University of Illinois at Chicago |
| UI Health | University of Illinois Hospital and Health System |
| V_{max} | Maximal Hepatic Degradation Rate |
| V_P | Extrahepatic Distribution Volume |

1.0 Project Summary/Abstract

Polycystic Ovary Syndrome (PCOS) is characterized by hyperandrogenism, ovulatory dysfunction and polycystic ovaries. Insulin resistance (IR) is a common feature of PCOS, and the resultant hyperinsulinemia has been theorized to promote hyperandrogenism in the disorder. However, 30-50% of women with PCOS who are lean do not have insulin resistance. Women with PCOS also exhibit chronic low-grade inflammation. We have shown that in PCOS, glucose ingestion activates nuclear factor κ B (NF κ B), the cardinal signal of inflammation culminating in upregulation of the inflammation pathway within mononuclear cells (MNC). This phenomenon is independent of excess adiposity and is highly correlated with circulating androgens. In addition, *in vitro* exposure to proinflammatory stimuli is capable of directly stimulating ovarian theca cell androgen production. Salicylate administration has been shown to suppress NF κ B activation, and the nonacetylated form of salicylate is well tolerated in humans.

The proposed research is a randomized double-blind placebo-controlled study of 90 women with PCOS. Forty-five subjects with PCOS (15 lean without IR), 15 lean with IR and 15 obese) receiving salsalate, a nonacetylated salicylate, at an oral dose of 3-4 gm daily for 12 weeks will be compared with 45 age- and body-composition-matched control women with PCOS receiving placebo (Fig. 1). The *overarching hypothesis* is that inflammation contributes to ovarian dysfunction, independent of excess adiposity or IR.

The *specific aims* are, I: To examine the effect of salsalate administration on the ovarian capacity to secrete androgen and insulin sensitivity in PCOS. II: To examine the effect of salsalate administration on the inflammatory response of mononuclear cells induced by lipid ingestion and glucose infusion in PCOS. The *approach* involves evaluation of ovarian androgen secretion in response to human chorionic gonadotropin administration and insulin sensitivity during the insulin-modified frequently sampled intravenous glucose tolerance test (FS-IVGTT) along with ovulation monitoring before and after salsalate administration. The inflammatory response of MNC to lipid ingestion will also be evaluated during treatment by measuring reactive oxygen species, the mRNA and protein content of inflammation markers, NF κ B activation and cytokine release in culture.

It is our *expectation* that women with PCOS receiving salsalate will exhibit decreased ovarian androgen secretion and reduced inflammation regardless of the degree of adiposity or IR status. These results will be significant because they will show a causal contribution of inflammation to ovarian dysfunction in PCOS, thereby improving our understanding of the pathogenesis of PCOS; open previously unexplored therapeutic avenues that are not necessarily dependent on improving IR; and guide the design of future studies aimed at determining what dietary modifications, medical regimen or both will optimally attenuate inflammation in PCOS to reduce medical disease and enhance fertility.

2.0 Background/Scientific Rationale

PCOS is characterized by hyperandrogenism, ovarian dysfunction and polycystic ovarian morphology.¹ Obesity and IR are common features of PCOS.^{2,3} Under the current model of pathophysiology of PCOS, the compensatory hyperinsulinemia of IR is the primary driver of hyperandrogenism. This concept was born from the cross-sectional observation that insulin is positively correlated with androgens in obese women with PCOS,² and is supported by reports of increased androgen production from theca cells obtained from obese women with PCOS following insulin exposure *in vitro*⁴ and increases in circulating androgens in women with PCOS following insulin infusion *in vivo*.⁵⁻⁷ However, these *in vitro* - *in vivo* responses were elicited with supraphysiological insulin concentrations.⁴⁻⁷

Physiological insulin infusion on the other hand does not augment androgen levels in PCOS.⁶ The current model also does not explain the cause of hyperandrogenism and ovarian dysfunction in the 30-50% of women with PCOS who are lean and lack IR. Thus, some other factor contributes to these abnormalities in PCOS.

We have shown that ingestion of glucose and saturated fat elicits an inflammatory response from circulating MNC in lean women with PCOS who lack excess abdominal adiposity. The hallmark of this response is increased activation of NF κ B, the cardinal signal of inflammation (Fig. 2).⁸⁻¹¹ These findings illustrate the separate and discrete role of MNC in manifesting inflammation in PCOS and that MNC are an excellent model to assess systemic inflammation in PCOS.

We have also shown that in PCOS, there is a link between molecular markers of inflammation from MNC and circulating androgens.⁸⁻¹⁴ Chronic suppression of ovarian androgen production does not ameliorate inflammation in lean women with PCOS.¹⁵ However, *in vitro* exposure of ovarian theca cells to proinflammatory stimuli upregulates CYP17, the androgen producing enzyme and increases testosterone.^{16,17}

Salsalate is an inexpensive, safe, well-tolerated, well-understood anti-inflammatory agent that inhibits NF κ B activation when used at higher doses.^{18,19} The salsalate dose required to achieve a salicylate level in the upper therapeutic range is dependent on body mass.²⁰ This is achieved in lean individuals using 3.0 gm/day as the maximum dose recommended in the salsalate package insert. Individuals across the obese range (30-40 kg/m²) require >3.0 gm/day to achieve the same objective.^{21,22} Salsalate and other salicylates have also been shown to decrease IR.^{19,23,24} However, the ability of salsalate to decrease IR would not be necessary if the beneficial anti-inflammatory effect of salsalate to reduce hyperandrogenism is on the ovaries. In fact, we have shown that in lean insulin-sensitive women with PCOS, salsalate reduces human chorionic gonadotropin (HCG)-stimulated ovarian androgen secretion by 44% and normalizes basal testosterone levels.²⁵ Our studies in MNC also confirm the ability of salsalate to suppress NF κ B activation.²⁵ Together these observations validate the use of these measurements as endpoints to assess the effects of salsalate to probe the pathophysiology of PCOS.

[figure not shown]

Fig.2. Gel shifts depicting the activation of MNC-derived NF κ B, the cardinal signal of inflammation, following glucose ingestion in lean women with PCOS with and without excess abdominal adiposity and body composition-matched controls. Results are expressed as change

Salsalate raises circulating insulin due to its ability to decrease insulin clearance from the liver which confounds the assessment of insulin sensitivity from post-treatment hyperinsulinemic-euglycemic clamp studies.^{19,23,26} Performance of a novel minimal model-based analysis from an insulin-modified FS-IVGTT is able to address this confounding factor. With this approach, hepatic and extrahepatic insulin clearance can be estimated before and after salsalate treatment to obtain measures of insulin sensitivity that take into account the salsalate-induced alteration in insulin clearance. The FS-IVGTT using the minimal model approach has been used for nearly four decades as a metabolic research tool and has been widely published.²⁷⁻³² A co-investigator ([name]) is experienced in the performance of the minimal model FS-IVGTT.^{33,34}

In this context, the *rationale* for the proposed study revolves around the concept that in PCOS, inflammation contributes to ovarian dysfunction independent of excess adiposity or IR, and may also improve insulin sensitivity when IR is present. We propose to undertake a 12-week randomized, double-blind, placebo-controlled trial to test the link between inflammation and ovarian androgen secretion in PCOS unrelated to IR. If this study of pathophysiology demonstrates beneficial effects, this will pave the way for developing novel therapies for ovarian dysfunction in PCOS.

3.0 Objectives / Aims

The *main objective of this proposal* is to evaluate the ability of salsalate to reduce ovarian androgen secretion, induce ovulation and decrease lipid- and glucose-stimulated inflammation independent of body composition and IR in women with PCOS; and to also improve insulin sensitivity in IR women with PCOS. Effects of salsalate will be assessed based on the following aims:

Specific Aim 1. To examine the effects of salsalate administration on the ovarian capacity to secrete androgens, menstrual function, and insulin sensitivity in PCOS.

The *hypothesis* for this aim is that salsalate treatment will decrease HCG-stimulated ovarian androgen secretion and induce ovulation in women with PCOS regardless of body composition or IR status; and may also improve insulin sensitivity in IR women with PCOS. We will test this hypothesis in a randomized double-blind placebo-controlled study. The ovarian androgen response to HCG administration will be evaluated in women with PCOS (15 lean with IR, 15 lean without IR and 15 obese) before and after administration of a therapeutic salsalate dose for ~12 weeks compared with women with PCOS receiving placebo for ~12 weeks (15 lean with IR, 15 lean without IR and 15 obese). Ovulation monitoring will occur in all subjects using timed progesterone measurements and serial follicular ultrasonography as indicated. Fractional glucose disappearance per insulin concentration unit adjusted for insulin clearance will be determined as a measure of insulin sensitivity (S_I) during a FS-IVGTT before and after salsalate or placebo administration. We anticipate that salsalate will reduce the exaggerated ovarian androgen response to HCG administration and lead to hormonal and sonographic evidence of ovulation regardless of body composition or IR status when compared with placebo. We also anticipate that salsalate will increase S_I in IR women with PCOS compared with placebo.

Specific Aim 2. To examine the effect of salsalate administration on the inflammatory response of mononuclear cells induced by lipid ingestion and glucose infusion in PCOS.

The *hypothesis* for this aim is that salsalate administration will down-regulate inflammatory signal transduction and cytokine production within MNC following lipid ingestion and glucose

infusion in women with PCOS regardless of body composition or IR status. We will test this hypothesis using the study design described in Aim 1. The inflammatory response of MNC to a cream challenge test will be evaluated in women with PCOS before and after salsalate treatment with the following measurements: a) reactive oxygen species (ROS) generation; b) NF κ B activation; c) mRNA and protein proinflammatory markers; d) cytokine release from cultured MNC culture. It is anticipated that lipid- and glucose-induced inflammation will decrease with salsalate use regardless of body composition or IR status when compared with placebo.

4.0 Eligibility

The protocol will prospectively study healthy reproductive-age women with PCOS recruited from clinical practice or various local advertisements (see section 5.0). Volunteers interested in study participation will respond by telephone or secure e-mail (see section 5.0). They will subsequently be provided with a detailed study description and undergo an initial pre-screening using questions from an eligibility assessment form (attached). During the prescreening, volunteers will be asked to provide their name, contact information, age/date of birth, smoking status, and information about their current medical conditions, general and gynecological health status and medication use. All of the answers obtained will be documented in the eligibility assessment form which will be kept in each volunteer's study booklet. The PI will determine subject eligibility based upon the following inclusion / exclusion criteria.

4.1 General Inclusion Criteria:

- Diagnosis of PCOS based on the presence of hyperandrogenism (skin manifestations of androgen excess such as hirsutism, acne or temporal balding – or –elevation of at least one serum androgen [i.e. total testosterone, free testosterone, androstenedione or DHEA-S] using predetermined local laboratory cutoffs), oligo/amenorrhea and evidence of withdrawal bleeding after progestin administration.
- 18-40 years of age.
- Good health as evidenced by medical history, physical examination and gynecologic examination within 30 days prior to starting the study.
- Willingness to provide informed consent according to the guidelines of the University of Illinois at Chicago (UIC) Institutional Review Board (IRB).
- Willingness to use double-barrier contraception such as condoms and topical spermicide (foam, cream or gel), condom and diaphragm, diaphragm and topical spermicide or sponge with topical spermicide if sexually active. Use of a non-hormonal intrauterine device (IUD), or permanent sterilization of the subject or her partner (i.e. tubal ligation or vasectomy) is also acceptable in all instances.

4.2 General Exclusion Criteria:

- Hyperprolactinemia.
- Uncontrolled thyroid disease.
- Evidence of Cushing's syndrome, nonclassic congenital adrenal hyperplasia or a hormone producing tumor based on physical findings and serum androgen levels on initial screening.
- Known or suspected pregnancy.
- Regular vigorous physical activity during previous 6 months.
- Use of any medications known to affect carbohydrate or sex hormone metabolism such as oral contraceptives, progestins, glucocorticoids or insulin sensitizing agents within 30 days of beginning the study.

- Acute or chronic inflammatory illnesses (e.g. URI, asthma, rheumatoid arthritis or systemic lupus erythematosus).
- Type 1 or type 2 diabetes mellitus defined as having a fasting glucose >126 mg/dl and/or a 2-hour postprandial glucose >200 mg/dl.
- Regular smoking defined as more than 2 cigarettes a month, or any smoking within 30 days of beginning the study.
- History of any illness exacerbated by salicylate use (e.g. peptic ulcer hepatic or renal disease, anemia, thrombosis, coagulopathy, congestive heart failure, hypertension or gout).
- Allergy to salicylate or dairy products.
- Medication use interacting with salicylates such as anti-platelet drugs (e.g. cilostazol, clopidogrel), anticoagulants (e.g. enoxaparin, heparin, warfarin), corticosteroids (e.g., prednisone), certain diabetes drugs (e.g. sulfonylureas such as glyburide), certain anti-seizure drugs (e.g. phenytoin, valproic acid), cidofovir, cyclosporine, drugs for gout (e.g. probenecid, sulfipyrazone), anti-hypertensives (e.g. ACE inhibitors such as captopril, angiotensin II receptor antagonists such as losartan, and beta blockers such as metoprolol), drugs that affect the acidity of urine (e.g. ammonium chloride, acetazolamide), lithium, methotrexate, oral bisphosphonates (e.g. alendronate), pemetrexed, SSRI antidepressants (e.g. fluoxetine, sertraline), tenofovir, and diuretics (furosemide, hydrochlorothiazide, spironolactone).

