6.0 Study Design and Procedures

This research will involve the prospective study of 90 reproductive age women (18-40 years) with PCOS using a randomized double-blind placebo-controlled study design. The randomization schedule will be stratified by body mass index (BMI) (lean: BMI ≥ 18 but ≤ 25 kg/m²; obese: BMI ≥ 30 but ≤ 40 kg/m²) and IR status study groups to ensure a balance of patients in the two study arms. IR will be defined by the insulin area under the curve from 0-120 min (insulin AUC₀₋₁₂₀) of an oral glucose tolerance test (OGTT) $> 7,000$ which is highly predictive and thus, recommended for population assessment of IR in PCOS.³⁵ Forty five (45) of the women with PCOS will receive salsalate of which 30 will be lean (15 without IR; 15 with IR) and 15 will be obese. The other 45 women with PCOS with a similar frequency distribution of BMI and IR status will receive placebo. Thus, the study will be comprised of the following 6 groups:

1. Salsalate-treated lean PCOS without IR (n=15)
 - BMI ≤ 25 kg/m² – and – 2-hour oral glucose tolerance test (OGTT) insulin area under the curve (AUC) $\leq 7,000$
2. Placebo-treated lean PCOS without IR (n=15)
 - BMI ≤ 25 kg/m² – and – 2-hour OGTT insulin AUC $\leq 7,000$
3. Salsalate-treated lean PCOS with IR (n=15)
 - BMI ≤ 25 kg/m² – and – 2-hour OGTT insulin AUC $> 7,000$
4. Placebo-treated lean PCOS with IR (n=15)
 - BMI ≤ 25 kg/m² – and – 2-hour OGTT insulin AUC $> 7,000$
5. Salsalate-treated Obese PCOS – BMI ≥ 30 kg/m² – ≤ 40 kg/m² (n=15)
6. Placebo-treated Obese PCOS – BMI ≥ 30 kg/m² – ≤ 40 kg/m² (n=15)

After the initial pre-screening, volunteers will be asked to come to the CCTS CRC at [name] for a screening visit at ~ 8:00 AM. The screening visit will occur within 1 to 4 weeks of beginning the study protocol and will last ~4 hours. At the start of the screening visit, volunteers will undergo informed consent followed by a complete history and physical, vaginal sonography, and blood draws for a hormonal evaluation if not performed previously, a complete blood count (CBC), a comprehensive metabolic panel (CMP) and an OGTT. Based on the screening results, volunteers deemed eligible for study participation will subsequently enter the study protocol beginning between days 3 and 13 following the onset of either a spontaneous or progestin-induced withdrawal bleed, or without regard to the onset of menses if vaginal

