6.1 Subject-Related Procedures

- *Screening* of volunteers to confirm the diagnosis of PCOS will typically be based on previously measured hormone levels. It is anticipated that most subjects with PCOS will be diagnosed by the PI just prior to study entry, and will likely involve performance of a hormonal evaluation within 6 months of beginning the study. However, the timing of previous hormone measurements used to diagnose PCOS will be left to the discretion of the PI. If the relevant tests for this purpose have not been performed previously, the necessary hormone levels will be obtained from a screening blood draw which will also be used to measure a CBC and CMP (maximum 22 ml). Assays to measure prolactin, TSH, LH, FSH, total testosterone, free testosterone, androstenedione, DHEA-S and 17-hydroxyprogesterone (17OHP) along with the CBC and CMP will be performed by the UI Health Clinical Pathology Laboratory. Pregnancy will be ruled out in all subjects immediately prior to study testing before and after treatment with salsalate or placebo using a urine test sensitive enough to detect >50 mIU/L of HCG.
- *Screening* of volunteers with an OGTT to rule out diabetes and to determine IR status will be performed in the CCTS CRC prior to study entry after an overnight fast of ~12 hours. A polyethylene intravenous catheter will be inserted in an arm vein for blood sampling at ~9:00 AM. The size of the catheter (i.e. 18-23-gauge) will be of suitable caliber for the size of the vein used to gain access. A baseline blood sample (9 ml) will be drawn in the fasting state. A 75 gram glucose beverage will subsequently be ingested over 10 minutes. Blood samples (9 ml each) will again be drawn at 30, 60, 90, 120 and 180 minutes following glucose ingestion. Every attempt will be made to insert the intravenous catheter and obtain blood samples on time. However, a sample may be obtained within a fifteen minute window after the scheduled time due to any unforeseen technical difficulty. Upon completion of the test, the indwelling catheter will be removed and subjects will be fed a high carbohydrate snack. Blood glucose and plasma insulin levels will be measured by the UI Health Clinical Pathology Laboratory.

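### The 30-day drug-free rule runs from study start, not from the screening OGTT 1 to 4 weeks earlier, so a lean woman's IR label may reflect recent drug use

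*Combined protocol and SAP*

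**What the plan says.** All references are to the combined protocol and SAP.

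- **Drug exclusion.** Section 4.2 lists, among drugs that act on carbohydrate or sex hormone metabolism, "oral contraceptives, progestins, glucocorticoids or insulin sensitizing agents within 30 days of beginning the study".
- **Timing of screening.** Section 6.0: "The screening visit will occur within 1 to 4 weeks of beginning the study protocol and will last ~4 hours". The OGTT is part of that visit.
- **Order of events.** Section 6.0 continues: "Based on the screening results, volunteers deemed eligible for study participation will subsequently enter the study protocol". The first protocol week then holds Visits 1 to 5; screening is not one of them.
- **Purpose of the OGTT.** Section 6.1 describes screening with an "OGTT to rule out diabetes and to determine IR status will be performed in the CCTS CRC prior to study entry".
- **Use of the result.** Section 6.0: "IR will be defined by the insulin area under the curve from 0-120 min" of the OGTT, with a cut-off of 7,000. Randomisation is stratified by BMI and IR status. IR status divides only the lean women; obese women form one group whatever their OGTT shows.
- **Analysis.** Sections 12.2 and 12.3(ii) make salsalate versus placebo within lean non-IR, lean IR and obese women the three primary contrasts. The S_I comparison is limited to lean IR and obese women.

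Nothing in the text available sets a drug-free interval before the OGTT, or asks for IR status to be checked again at Visit 1.

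**The concern.** The plan treats these drugs as able to disturb carbohydrate metabolism and asks for 30 days without them. It counts those days back from the start of the study, but the test that most needs the protection is taken before that date. The screening OGTT is the only measurement that separates lean IR from lean non-IR women, and it is also the diabetes screen.

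The overarching hypothesis (Section 1.0) is that inflammation contributes to ovarian dysfunction independently of adiposity and IR. The lean non-IR group carries the IR part of that argument. If some of its members fell below 7,000 because of a drug they had only just stopped, a salsalate effect there is weaker evidence that IR is not needed. Error the other way would put non-IR women into the lean IR contrast and the S_I analysis.

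**Working it through.** The plan states no drug-free time at the OGTT, so there is no figure to reproduce. The check is date arithmetic plus a reading of what study start means.

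**1. Which date the 30 days run from.** The phrase is not formally defined. Three places put screening before it:
- Section 6.0 dates the screening visit relative to the start of the protocol and has women enter afterwards.
- Section 6.1 puts the OGTT ahead of study entry.
- Section 4.1 requires good health shown by history, "physical examination and gynecologic examination within 30 days prior to starting the study", and Section 6.0 carries out the history and physical at screening.

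The consistent reading is that the study begins at Visit 1.

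**2. Minimum drug-free time at the OGTT.** Inputs: 30 days (Section 4.2) and a lead of 1 to 4 weeks (Section 6.0).

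Minimum days off drug at OGTT = 30 − 7 × (weeks from screening to start)

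| Screening before start | Minimum days off drug at OGTT |
|---|---|
| 1 week | 30 − 7 = 23 |
| 2 weeks | 30 − 14 = 16 |
| 3 weeks | 30 − 21 = 9 |
| 4 weeks | 30 − 28 = 2 |

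**3. Who is affected by the label.** Lean groups: 4 × 15 = 60 of 90 women. Two of the three primary contrasts depend on the label. The S_I set is 30 lean IR plus 30 obese women, so half of it (30 of 60) is selected by the OGTT and half by BMI alone.

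**4. Effect of moving the anchor.** If the 30 days were counted back from the OGTT, the minimum would be 30 days at the OGTT and 30 + 7 = 37 to 30 + 28 = 58 days at study start. The earliest permitted OGTT would move later by 30 − 23 = 7 to 30 − 2 = 28 days.

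**5. What cannot be computed.** If a residual effect lowered insulin AUC by a fraction x, a lean woman with a drug-free AUC between 7,000 and 7,000/(1 − x) would be labelled non-IR. The documents give no x, no distribution of AUC near the cut-off, and no count of women who recently stopped such drugs. No number of mislabelled women follows.

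**6. A related conflict.** Section 4.2 lists progestins in the same 30-day exclusion, while Section 6.0 allows entry on days 3 to 13 after a progestin-induced bleed. Both can hold only if the bleed starts at least 30 − 13 = 17 days (entry on day 13) to 30 − 3 = 27 days (entry on day 3) after the last progestin dose. The plan does not address this.

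**The case against.** **In the plan's defence.** Two days needs a woman who stops exactly 30 days before Visit 1 and is screened at the full four weeks. Pre-screening (Section 4.0) already records medication use, so the team would know of recent use when booking the OGTT. The eligibility forms that carry this check are listed as appendices but their text is not available; they may defer such women. This stands as a limit on how often the gap would open in practice. It does not close the gap in the protocol text. The separate list of drugs interacting with salicylates in Section 4.2 names corticosteroids and sulfonylureas but gives no time window, so it sets no interval before the OGTT either.

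**Stronger readings that the documents do not support.**
- *The primary comparisons are biased.* They are not. The label is set before randomisation and the contrasts are between arms within a stratum, so a wrong label falls on both arms by chance.
- *The error cannot be examined later.* The randomisation stratum is fixed, but every woman has a baseline FS-IVGTT at Visit 5, after the full 30 days, and Section 12.3(i) already compares baseline insulin sensitivity across the six groups. That comparison looks at group averages and would not by itself show individual wrong labels, but the data are there.
- *The 25% fall shows the size of the problem.* Section 12.2 reports testosterone AUC falling from 4395 to 3288 with an insulin sensitizer (1 − 3288/4395 = 25%). That is an effect of treatment on testosterone, not a residual effect on OGTT insulin after stopping. The HCG test starts at Visit 1, where the 30-day rule already applies.
- *The PCOS diagnosis is equally exposed.* Section 6.1 expects diagnosis mostly from earlier hormone results, with timing left to the investigator, and Section 4.1 accepts skin signs alone for hyperandrogenism. The point is much weaker there.

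**Conclusion.** The point holds as a gap in timing. As written, a compliant woman may be sorted at the 7,000 cut-off after a minimum of 2 days (worst case) to 23 days off drug, against the 30 days the plan requires at study start. This touches the IR label of lean women, 60 of 90, and the lean half of the S_I analysis set. It weakens what lean IR and lean non-IR mean, and so the conclusion that an effect does not depend on IR. The validity of the randomised comparisons, the type I error and the stated power are not in question.

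This rests on two assumptions: that the study begins at Visit 1, which Sections 4.1, 6.0 and 6.1 support without defining it; and that the unseen eligibility forms do not already set an interval before the OGTT. The size of any misclassification is unknown and could be small. The point is worth correcting because the correction is cheap, not because harm has been shown.

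**What to change.** 1. **Reconcile Sections 4.2, 6.0 and 6.1** so that the plan's existing 30-day interval also applies to the screening OGTT, and define the start of the study. Where a woman has used a listed drug too recently, defer the screening visit. No repeat OGTT is needed. This uses the plan's own interval; no other length is proposed.
2. **Add a sensitivity analysis to Section 12.3(ii)** for the lean IR and non-IR contrasts, using the baseline S_I from Visit 5. The documents give no S_I cut-off for IR, so the simplest form keeps S_I continuous: among lean women, replace the IR label and its interaction with treatment by baseline S_I and its interaction with treatment. Compare the result with the planned contrasts.
3. **Settle the progestin conflict in the same amendment.** The exclusion in Section 4.2 and the entry route in Section 6.0 must be reconciled, or the revised timing will carry the conflict into the screening period. Which rule should stand is for the sponsor and the investigator.

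**Cost.** A short amendment and one extra analysis on data already collected, with no added patients or procedures. Screening is delayed by up to about 4 weeks (at most 28 days) for women who recently stopped such drugs, and their minimum time off drug at study start becomes 37 to 58 days.
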